8.5 Dosage schedule

A single PDT session will be applied according to the study design described in Section 6.1, Section 8.3 and Figure 1.

8.6 Treatment assignment

This is a non-randomized, open-label study, i.e., all eligible subjects will receive active treatment.

8.7 Blinding, packaging, and labeling

This is an open-label study. i.e., blinding is not applicable.

8.7.1 Investigational medicinal product

The sponsor will ascertain that all study medication is manufactured and packaged in accordance with regulatory requirements and the principles of Good Manufacturing Practice (GMP).

Responsible for manufacturing and release of BF-200 ALA:

Biofrontera Pharma GmbH
[name]
[name]
Germany

The appropriate number of tubes and card board boxes will be labeled in English according to the pre-defined distribution of treatment numbers. The labels will include all information required by 21 CFR 312.6 (including the statement: “Caution: New Drug—Limited by Federal (or United States) law to investigational use”).

For each subject, a card box is provided containing three tubes with BF-200 ALA. Each box is labeled with a tear-off label and can be identified and assigned to a specific subject by a unique identification number.

In addition, each tube will be labeled accordingly. This label information must be documented in the appropriate space in the subject’s source data when the IMP is dispensed prior to PDT.

Additional statements may be printed on the label as required by local regulations.

The sponsor will maintain a complete record of batch numbers and expiry dates of the IMP and the labels of the IMP in the Trial Master File (TMF).

8.7.2 Investigational medical device

BF-RhodoLED® will be distributed and assembled/maintained at the sites by technicians or other properly trained delegates of:

Biofrontera Inc.

[name]
[name]
USA

The appropriate number of lamps will be labeled in English as investigational device in accordance with 21 CFR 801.1 and 21 CFR 812.5. Labels will include:

- the name and place of business of the manufacturer, packer, and distributor
- the statement: “CAUTION Investigational device. Limited by Federal (or United States) law to investigational use”.
- and/or references to all relevant contraindications, hazards, adverse effects, interfering substances, warnings and precautions.

For the purpose of this study, the Phase I unit will be provided with at least two BF-RhodoLED® lamps. It is exclusively intended to be used in conjunction with study medication within the scope of clinical trials conducted by Biofrontera. As the lamp will be assembled on site by a technician or delegate of Biofrontera, there will be no immediate packaging available. All labeling will be applied directly to the lamp.

8.8 Supplies and accountability

After the study protocol was approved or accepted by the Institutional Review Board(s) (IRB(s)) and by FDA, the sponsor will initiate the study site which includes installation of at least two BF-RhodoLED® lamps, and thereafter supply the study site with study medication, together with all relevant documentation. The sponsor is responsible for delivery of the investigational products to the study site.

The investigator will inventory and acknowledge receipt of all shipments of the IMP and IMD. The investigator is responsible for maintaining documentation showing the amount of investigational products provided to the study site and the used IMP for each study subject. Discrepancies in accountability of the investigational products must be explained and documented. The monitor is responsible to verify the investigator's documentation on receipt, use, and return of the investigational products. The monitor will check drug and medical device accountability at the Phase I unit on an ongoing basis during the study. At the end of the study, all remaining study medication or empty tubes must be returned to the drug supplier acting on behalf of Biofrontera Pharma GmbH for disposal. The monitor will prepare a final report of accountability of the investigational products for filing in the investigator site file (ISF).

After the last subject completed the treatment and no further trials are planned, all lamps will be disassembled by a technician and returned to Biofrontera Inc. Receipt and return of BF-RhodoLED® will be acknowledged and documented accordingly.

8.9 Compliance

The application of study medication will be administered/supervised by the investigator or subinvestigator. Any delegation of this responsibility should follow the guidelines stated in Section 15.2.

The study medication will never be handed out to the subjects but applied by study personnel, rendering individual compliance assessments unnecessary.

BF-RhodoLED® lamps will be exclusively operated by previously trained study personnel.

9 PRIOR AND CONCOMITANT ILLNESSES AND TREATMENTS

9.1 Prior and concomitant illnesses

Additional diseases present at the time of signing the informed consent are regarded as concomitant diseases and must be documented in the eCRF. Relevant past diseases must also be documented in source data and in the medical history section of the eCRF.

Illnesses first occurring or detected during the study, and worsening of a concomitant disease during the study, are to be regarded as AEs and must be documented in source data and in the AE section of the eCRF (see Section 11).

9.2 Prior and concomitant treatments

Any medication taken by a subject at study entry or treatments the subject is undergoing throughout the study that are not related to any study-specific procedures (PDT with IMP), are considered concomitant treatments. The use of required concomitant treatments, which are known not to interfere with the IMP or to mask their effect, is unrestricted and may be continued during the study.

Inflammation triggered by the photodynamic reaction is an important part of the therapeutic principle and is intended. Therefore, intake of systemic anti-inflammatory drugs must be stopped prior to PDT, especially systemic corticosteroids and antiphlogistics (NSAIDs) (see Section 7.4 and below).

Nevertheless, the following treatments are permitted in the designated trial periods to alleviate pain and discomfort:

- During PDT
 - In cases where the pain is regarded as unbearable by the subject, the PDT may be interrupted and/or cooling with an air stream or nebulized water may be offered.
 - Severe cases of pain might require to briefly interrupt illumination, e.g. to inject a local, fast-acting anesthetic, such as xylocaine or to cool briefly with cooling packages.
- Treatment of pain and discomfort after PDT
 - Cooling the illuminated area(s) with wet or refrigerated compresses
 - Analgesic treatment with acetaminophen (e.g. Tylenol®)

Cooling compresses and acetaminophen (e.g. Tylenol®) should be offered by the study staff to all subjects after PDT for the purpose of pain management.

Further treatments are also allowed for the management of pain and discomfort but should be used as a second line treatment option:

- Topical corticosteroids
- Topical diclofenac up to 2.5 % outside the treatment field(s)

All concomitant treatments underwent/taken during the study must be documented in source data and on the appropriate pages of the eCRF along with the indication, single dose, route of administration, frequency of administration as well as start and stop date of administration.

The subject should confer with the investigator prior to the use of new medication during the course of the study.

The following concomitant treatments/procedures are not permitted:

- Any therapy such as cryotherapy, laser therapy, electrodesiccation, surgical removal of lesions, curettage, or treatment with chemical peels such as trichloroacetic acid within the treatment field(s), or within a radius less than 5 cm away from the treatment field(s) 4 weeks prior to screening and throughout the study. Non-target lesions may be treated with these methods if the distance to the treatment field is more than 5 cm.
- A list of forbidden, concomitant medication is provided in Table 4.

If the investigator, at any time in the study, suspects a lesion within or outside the treatment field(s) to have progressed into a manifest malignancy, they should refer the subject for standard medical treatment, irrespective of whether or not this results in exclusion of the subject from the study.

Table 4: List of forbidden concomitant medication with designated time periods.

Medication	Topical administration ^a	Systemic administration		
	start of restriction	forbidden until	start of restriction	forbidden until
ALA or ALA-esters (except IMP at Visit 2)	8 weeks prior to Visit 1	end of study	12 weeks prior to Visit 1	end of study
Cytotoxic drugs	8 weeks prior to Visit 1 (within treatment field(s)) ^b	end of study (within treatment field(s)) ^b	24 weeks prior to Visit 1	end of study
Immunomodulators/immunosuppressive therapies	8 weeks prior to Visit 1 (within treatment field(s)) ^b	end of study (within treatment field(s)) ^b	12 weeks prior to Visit 1	end of study
	7 days prior to PDT (within and outside treatment field(s))	end of study (within and outside treatment field(s))		
Interferon	---	---	6 weeks prior to Visit 1	end of study
Corticosteroids	(allowed)	(allowed)	6 weeks prior to Visit 1 ^d	end of study ^d
NSAIDs	7 days prior to PDT ^c	7 days post PDT ^c	7 days prior to PDT	7 days post PDT
Acetylsalicylic acid > 100 mg/day	---	---	7 days prior to PDT	7 days post PDT
Ibuprofen > 200 mg/day	---	---	7 days prior to PDT	7 days post PDT

Medication	Topical administration ^a	Systemic administration		
	start of restriction	forbidden until	start of restriction	forbidden until
Diclofenac (> 2.5 %)	8 weeks prior to Visit 1 (within treatment field(s)) ^b	end of study (within treatment field(s)) ^b	7 days prior to PDT	7 days post PDT
Hypericin or drugs with phototoxic/ photoallergic potential^c	8 weeks prior to Visit 1	end of study	8 weeks prior to Visit 1	end of study
Investigational drugs	8 weeks prior to Visit 1	end of study	8 weeks prior to Visit 1	end of study
Drugs known to have major organ toxicity	---	---	8 weeks prior to Visit 1	end of study
Medication that influence coagulation (e.g. anticoagulants, anti-platelet drugs)	---	---	Visit 1 (may be used throughout the study if taken in a dose stable prior to study)	end of study (may be used throughout the study if taken in a dose stable prior to study)
EMLA® cream	Visit 2 (within treatment field(s)) ^b	7 days post PDT (within treatment field(s)) ^b	---	---

^a Within and outside the treatment field(s).

^b Restriction is limited to the use within treatment field(s) and surrounding skin areas within a radius less than 5 cm away from the treatment field(s).

^c Topical use of diclofenac up to 2.5 % may be used outside treatment field(s) throughout the study.

^d For oral or injectable corticosteroids.

^e Start of therapy with any photosensitizer or systemically-acting drugs with phototoxic or photoallergic potential, such as psoralenes, tetracyclines, nalidixic acid, furosemide, amiodarone, phenothiacyclines, chinolones, fibrates, or phytotherapy with St. John's wort, arnica, or valerian or topically applied phototoxic substances like tar, pitch, psoralenes or some dyes like thiazide, methylene blue, toluidine blue, eosin, rose bengal, or acridine within 8 weeks prior to screening. Subjects may, however, be eligible if such medication was taken in 8 weeks prior to screening without evidence of an actual phototoxic/photoallergic reaction. These medications must not be newly prescribed within 8 weeks prior to screening. If such a prescription becomes unavoidable for medical reasons in between Visit 2 and Visit 3, the study participation of the affected subject should be continued regularly.

10 STUDY PROCEDURES AND SCHEDULE

10.1 Description of study days

Table 1 summarizes the study schedule.

10.1.1 Screening visit (\leq 14 days prior to PDT)

Potential subjects will be evaluated to determine if they fulfill the inclusion and exclusion criteria (see Sections 7.3 and 7.4). The following evaluations and procedures will be performed at Visit 1 (screening) and recorded in the eCRF:

NOTE: In case the subjects come to the screening visit in a fasted state, blood and urine sampling will be performed. In case the subject is not fasted, blood and urine sampling will be postponed 1-2 days.

[figure not shown]
- Obtain informed consent prior to any study-related procedures.
- Assign subject number
- Document concomitant diseases and relevant medical history
- Document AK history
- Obtain demographic data
- Check inclusion and exclusion criteria
- Assess skin type according to Fitzpatrick, 1988 (38)
- Select treatment field(s) and assess target lesions (size, number, location and clinical assessment according to Olsen et al., 1991 (37))
- Generate template of AK treatment field(s) on provided grid foil and sketch treatment field(s) and suggested illumination area(s) into cartoon (to be kept in the subject file)
- General physical examination
- Measure vital signs (HR, BP)
- Fasting clinical laboratory tests (including routine hematology, blood chemistry, serum pregnancy tests, coagulation parameters, eGFR and urinalysis)
- Hepatitis and HIV serology.
- Blood sampling for ALA and PpIX baseline levels
- Documentation of (S)AEs.
- Instruct subject about forbidden concomitant treatments (see Section 9.2).

10.1.2 Visit 2/Baseline (PDT)

The following procedures will be performed at Visit 2 and recorded in the eCRF:

- Reevaluation of inclusion and exclusion criteria for confirmation of subject's eligibility
- Evaluation of dosing day exclusion criteria

- Explanation of allowed/forbidden medication 7 days after PDT to subjects (see Section 9.2 and Table 4)
- Measurement of vital signs (HR and BP) prior to PDT
- Pregnancy test (urine) for females of reproductive potential prior to PDT
- Blood sampling for ALA and PpIX analysis: In total, 14 blood samples will be collected at the time points defined below (Figure 2)
- Preparation of treatment field(s) and application of BF-200 ALA and occlusive, light-blocking dressing according to treatment description in Section 8.3
- Date and time of study drug application and removal will be recorded in source data and in the eCRF
- Illumination of treatment field(s) with the BF-RhodoLED® lamp until a total light dose of 37 J/cm² is achieved (according to treatment description in Section 8.4). In case of discontinuous treatment field(s), two BF-RhodoLED® lamps are used simultaneously, such that for the entire 60 cm² surface only one illumination step is performed
- Duration of illumination and distance between the BF-RhodoLED® lamp and the treatment field(s) will be documented in source data and in the eCRF. Otherwise, reasons for not meeting the requirements must be given. The duration, reason, and frequency of any interruptions must be recorded in the subject's source data and the eCRF. Pain relieving measures should be documented accordingly, if applicable
- Documentation of concomitant medications/treatments (e.g. for pain management) that might be required during or after PDT (see Section 9.2 and Table 4)
- Assessment of application site pain during PDT via NRS-11 (should be performed in between the blood sampling time points 3.5 h and 4 h after application of BF-200 ALA)
- (S)AEs including application site skin reactions, application site discomfort, pain during and post PDT, and new lesions in the treatment field(s) (assessment of pain after PDT should be performed as described in Section 10.2.7 before discharge of the subject)
- Reinform subjects about restrictions to intensive UV-radiation for 48 h (please see also Section 8.4 for detailed information)

*Blood sampling time points are specified in hours relating to the time point of BF-200 ALA application. Timepoint 0 is defined as the start of the application of BF-200 ALA.

Figure 2: Time points for PK blood sampling at Visit 2.

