1. Subjects with at least 12 distinctive and clinically confirmed mild to severe AK lesions (according to Olsen et al., 1991) with a diameter of \geq 4 mm each, on either the face/scalp (including forehead, excluding eyes, nostrils, ears, and mouth) or the neck/trunk/extremities, within treatment field(s) of about 60 cm² in total. Treatment field(s) may be discontinuous but must be within 2 illumination areas of the BF-RhodoLED® lamp (6 cm x 16 cm each).
2. All genders 18 - 85 years of age (inclusive).
3. Willingness and ability of the subject to provide informed consent and to sign the Health Insurance Portability and Accountability Act (HIPAA) form. A study-specific informed consent form and HIPAA form must be obtained in writing for all subjects prior to starting any study procedures.
4. Willingness and ability to comply with study procedures, particularly willingness to receive one PDT with up to two illumination devices simultaneously.
5. Subjects with good general health and subjects with clinically stable medical conditions will be permitted to be included in the study.
6. Subjects receiving any drugs affecting coagulation (e.g. anticoagulants, anti-platelet drugs) should be on a stable dose.
7. Acceptance to abstain from extensive sunbathing and the use of a solarium during the clinical study.
8. Women of child-bearing potential must have a negative serum pregnancy test and must use an adequate and highly effective or two effective methods of contraception throughout the study.

Exclusion criteria:

To reduce risks for the subjects and to ensure that the subjects are in a comparable status, subjects will be excluded if they meet at least one of the following exclusion criteria:

1. Any known history of hypersensitivity to ALA, porphyrins or excipients of BF-200 ALA.
2. History of soy or peanut allergy.
3. Subjects with sunburn within illumination areas (reassessment of subjects is allowed once if the sunburn is expected to resolve within the screening period. Reassessment can be done on the day of the actual treatment).
4. Clinically significant medical conditions making implementation of the protocol or interpretation of the study results difficult or impairing subjects' safety such as:
 - a. Presence of porphyria or known photodermatoses
 - b. Known diagnosis of human immunodeficiency virus (HIV) based on clinical history
 - c. Metastatic tumor or tumor with high probability of metastasis
 - d. Infiltrating skin neoplasia (suspected or known).

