7.3 Inclusion criteria

Eligible subjects must meet the following criteria:

1. Subjects with at least 12 distinctive and clinically confirmed mild to severe AK lesions (according to Olsen et al. 1991 (37)) with a diameter of ≥ 4 mm each, on either the face/scalp (including forehead, excluding eyes, nostrils, ears, and mouth) or the neck/trunk/extremities, within treatment field(s) of about 60 cm^2 in total. Treatment field(s) may be discontinuous but must be within 2 illumination areas of the BF-RhodoLED® lamp ($6\text{ cm} \times 16\text{ cm}$ each).
2. All genders 18-85 years of age (inclusive).
3. Willingness and ability of the subject to provide informed consent and to sign the Health Insurance Portability and Accountability Act (HIPAA) form. A study-specific informed consent form and HIPAA form must be obtained in writing for all subjects prior to starting any study procedures.
4. Willingness and ability to comply with study procedures, particularly willingness to receive one PDT with up to two illumination devices simultaneously.
5. Subjects with good general health and subjects with clinically stable medical conditions will be permitted to be included in the study.
6. Subjects receiving any drugs affecting coagulation (e.g. anticoagulants, anti-platelet drugs) should be on a stable dose.
7. Acceptance to abstain from extensive sunbathing and the use of solarium during the clinical study.
8. Women of child-bearing potential must have a negative serum pregnancy test and must use an adequate and highly effective or two effective methods of contraception throughout the study.

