The subject should be informed about restrictions defined in Table 4 and in Section 9.2.

A surgical dressing of the treated area is normally not required and should be avoided whenever possible.

Although a nearly complete loss of PpIX by photobleaching is assumed to occur during PDT, subjects should avoid exposure to intensive sun light for about 48 h since new PpIX may accumulate from remaining ALA. Additional light exposure may enhance the typical side effects of PDT. Subjects should not expose themselves to intensive ultraviolet (UV)-radiation

(solarium, sun bathing, etc.) during the course of the study (see also Section 7.4) to avoid UV-induced post inflammatory hyperpigmentation of the healing tissue.

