11.2 Period of AE collection

Collection of AEs starts with signing the informed consent documents until the end of the study. AEs will be discriminated as AEs and TEAEs.

- AEs developing between signing the ICF until Visit 2 with a suspected causal relationship to any study procedures will be considered and documented as an AE.
- Collection of TEAEs extends from Visit 2 (baseline) until end of the study at Visit 3.
- If the investigators detect an SAE in a subject after end of study, and considers the event possibly related to prior study treatment or procedures, they should report this event to the pharmacovigilance department of the sponsor (see section 11.3.1).

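### The Visit 2 checklist limits the intensive-UV restriction to 48 h, whereas Section 8.4 and inclusion criterion 7 apply it for the whole study

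*Protocol*

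**What the plan says.** Four places in the protocol bear on this point.

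- **Section 10.1.2, Visit 2 procedures.** The list contains the reminder "Reinform subjects about restrictions to intensive UV-radiation for 48 h (please see also Section 8.4 for detailed information").
- **Section 8.4, first precaution.** After illumination, "subjects should avoid exposure to intensive sun light for about 48 h since new PpIX may accumulate from remaining ALA".
- **Section 8.4, second precaution.** "Subjects should not expose themselves to intensive ultraviolet (UV)-radiation", with solarium use and sunbathing given as examples, "during the course of the study (see also Section 7.4) to avoid UV-induced post inflammatory hyperpigmentation of the healing tissue".
- **Inclusion criterion 7.** Section 7.3 requires "Acceptance to abstain from extensive sunbathing and the use of solarium during the clinical study". The protocol outline in Section 2 has the same criterion: "Acceptance to abstain from extensive sunbathing and the use of a solarium during the clinical study".

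For an individual subject the study finishes at Visit 3. Section 11.2 says so in defining the adverse event period: "Collection of TEAEs extends from Visit 2 (baseline) until end of the study at Visit 3". Section 6.1 places Visit 3 at 28 (± 7) days after treatment.

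**The concern.** The two precautions in Section 8.4 differ in exposure, duration and reason. The Visit 2 line names UV, the exposure of the study-long rule, and gives it 48 h, the duration of the sunlight rule. It therefore states neither rule correctly: the UV rule is cut short, and sunlight, to which the 48 h belongs, is not mentioned.

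At stake is what subjects are told on the day of treatment. A subject reminded that UV matters for 48 h could conclude that sunbathing or a solarium is acceptable from day 3, while the treated skin may still be healing. This is a matter of subject protection and compliance. It does not touch the plasma concentrations, the sample size or any planned summary.

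**Working it through.** The plan states no figure to reproduce, so the check is a comparison of the texts followed by a short day count.

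**Step 1: the instructions side by side.**

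| Source | Exposure | Duration | Reason given |
|---|---|---|---|
| Section 8.4, first precaution | Intensive sunlight | About 48 h | PpIX may form again from residual ALA |
| Section 8.4, second precaution | Intensive UV (solarium, sunbathing) | Whole study | Hyperpigmentation of healing skin |
| Criterion 7 (Sections 2 and 7.3) | Extensive sunbathing, solarium | Whole study | None stated |
| Section 10.1.2 line | Intensive UV | 48 h | None stated; refers to Section 8.4 |

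The last row matches none of the rows above it. Nowhere else does the protocol put a 48 h limit on UV.

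**Step 2: could UV simply stand for sunlight?** Section 4.1 describes PpIX activation by blue to red light, with its maximum near 410 nm and smaller peaks near 510, 530, 580 and 630 nm. The 48 h precaution therefore concerns visible light. Calling it a UV restriction describes it incompletely.

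**Step 3: is it corrected elsewhere in the visit schedule?**
- Screening (Section 10.1.1) includes "Check inclusion and exclusion criteria", which covers criterion 7. Visit 2 repeats that check.
- The lists for the phone call (10.1.3) and Visit 3 (10.1.4) contain no light-exposure instruction. Nor do Table 1 and Section 10.3.
- Section 8.4 also sends staff to Table 4 and Section 9.2 for restrictions to explain to subjects. Those list medications and procedures and give no UV rule.

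The Visit 2 line is thus the only explicit light-exposure instruction after PDT in the visit lists.

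**Step 4: the size of the discrepancy.**
- Checklist: 48 h / 24 = 2 days.
- Section 8.4 and criterion 7: to Visit 3, from 28 − 7 = day 21 to 28 + 7 = day 35.
- Difference: 21 − 2 = 19 days to 35 − 2 = 33 days.
- Share of the post-PDT period covered by the checklist wording: 2/35 = 5.7% to 2/21 = 9.5%, or 2/28 = 7.1% at the nominal day.

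These figures compare two instructions. They do not estimate UV exposure or hyperpigmentation risk, for which the documents give no data.

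**The case against.** The strongest reply is that the line is a reminder and sets no rule. It asks staff to inform subjects again, it refers to Section 8.4 for detail, and Section 8.4 is unambiguous. Section 10.1.2 also sends staff to Section 8.4 for the illumination itself, so they can hardly carry out the visit without the correct text. On this view the line means the acute precaution after PDT, with UV written loosely for sunlight, and the study-long rule needs no repetition because the subject has already accepted it under criterion 7. Subjects also receive a written information sheet (Section 15.3). The day count should not be read as a period of risk either: Section 4.3 says that symptoms lasted 1 to 4 days in most cases, though sometimes 1 to 2 weeks or longer.

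Much of this stands, and it keeps the point small. Under-instruction would require the line to be taken literally and the references to Section 8.4 not to be followed. The day count is indeed only a difference between wordings.

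The mismatch itself remains. Even read as shorthand, the line names the wrong exposure. A line that already gives an exposure and a duration offers little reason to look further, and a subject could take a later reminder of 48 h as narrowing the earlier commitment. The content of the information sheet is not in these documents, so it cannot settle the matter.

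**Conclusion.** The concern holds. Section 10.1.2 combines two separate precautions into one that the rest of the protocol does not support, and it understates the UV restriction by 19 to 33 days relative to Section 8.4 and criterion 7. The practical risk is minor, because the correct rule is cross-referenced and criterion 7 is checked twice. There is no effect on the pharmacokinetic evaluation, the sample size or the analysis.

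The day count assumes that, for a subject, the study lasts until that subject's own Visit 3, as Section 11.2 indicates. Section 6.2 defines the end of the study overall as the last subject's last visit. On that reading the gap would be at least as long for every subject who completes Visit 3, and the conclusion would be unchanged.

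**What to change.** Reword the line in Section 10.1.2 along these lines: *remind subjects to stay out of intensive sunlight for about 48 h, and to avoid intensive UV (solarium, sunbathing) until Visit 3; see Section 8.4*. While doing so, confirm that the subject information sheet gives the same two durations.

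The cost is one checklist line. The new wording uses only rules already in Section 8.4 and criterion 7 and adds no requirement for subjects or staff. Section 15.6 classes the correction of inconsistencies as a non-substantial amendment.
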